5.9 Subject Replacement Strategy

A subject who discontinues from the trial will not be replaced.

5.10 Beginning and End of the Trial

The overall trial begins when the first subject signs the informed consent form. The overall trial ends when the last subject completes the last study-related phone-call or visit, discontinues from the trial or is lost to follow-up (i.e. the subject is unable to be contacted by the investigator).

5.11 Clinical Criteria for Early Trial Termination

Early trial termination will be the result of the criteria specified as follows.

5.11.1 Safety Criteria for Pausing Enrollment

If ≥ 3 subjects receiving MK-3682 and MK-8408 experience any of the following, assignment of new subjects into that arm will be paused. Subjects that are tolerating treatment may continue to receive study therapy, but no additional subjects will be enrolled into that arm until the Sponsor has reviewed all safety data on subjects, including:

- Life threatening clinical AEs, or an event that results in or prolongs an existing in-subject hospitalization, or deaths that are assessed to be study drug-related
- Grade 4 laboratory AEs that are assessed to be study drug-related laboratory AEs

5.11.2 Safety Criteria for Stopping Enrollment and Early Trial Termination

If a total of ≥ 12 subjects ($\sim 5\%$) in the 12-week arms of MK-3682+MK-8408 experiences any of the following, the trial will terminate.

- ALT or AST increases to >500 IU/L and is assessed to be study drug related
- The subject’s serum creatinine increases to Grade 3 or higher ($>1.8 \times$ upper limit of normal), confirmed with repeat test within 1 week
- The subject has a Grade 4 laboratory AE, or a life-threatening clinical AE, or an AE that results in or prolongs an existing in subject hospitalization, or death, that is assessed to be study drug-related
- The subject’s creatinine clearance decreases to <30 mL/min/1.73 m², confirmed with repeat test within 1 week. Creatinine clearance will be evaluated as an estimated GFR (eGFR), based on the modification of diet in renal disease (MDRD) equation:

$$\text{eGFR (mL/min/1.73 m}^2\text{)} = 175 \times (\text{Scr, std})^{-1.154} \times (\text{Age})^{-0.203} \times (0.742 \text{ if female}) \times (1.212 \text{ if black})$$

Scr, std: serum creatinine measured with a standardized assay

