All regimens were highly efficacious in subjects infected with GT3. Overall, 38/43 (88%) of subjects who received EBR and 40/43 (93%) of subjects who received MK-8408 achieved SVR₁₂. The MK-3682 (300 or 450mg)/GZR/MK-8408 regimens achieved SVR₁₂ among 93% (40/43) of GT3-infected subjects, despite baseline NS5A RAVs (defined as any change from wild-type at 10 positions (24, 28, 30, 31, 32, 38, 58, 62, 92, or 93)) in 47% (20/43) subjects. One of the 3 relapsers in these arms had a treatment-emergent NS5A RAV (Y93H) at the time of failure.

All 240 subjects completed the full 8 weeks of dosing. All regimens were generally well tolerated, and no cardiac or renal safety signals were identified. The frequency and severity of adverse events (AEs) were comparable among the four treatment groups. The most frequent study drug-related AEs were headache (23%), fatigue (20%), and nausea (13%). One subject (1/240, 0.4%) experienced an alanine aminotransferase (ALT) increase >5× the upper limit of normal (ULN) at TW8 with a pattern consistent with the late ALT increases observed in the Phase 2 and 3 GZR studies, which rapidly resolved off study drug. There were no drug-related serious adverse events (SAEs) and no subjects discontinued due to AEs. The results of Part A demonstrated that an 8-week regimen of MK-3682 (450mg)/GZR/MK-8408 was highly effective and well tolerated in GT1-, GT2-, and GT3-infected treatment-naïve, non-cirrhotic subjects, supporting the selection of this regimen from the four tested in Part A for further evaluation among a diverse population of HCV-infected subjects, including those with additional HCV GTs, cirrhosis, prior treatment, and HIV/HCV-co-infection.

In Part B of these studies, the combination regimen is being administered as FDC tablets (MK-3682B). Each MK-3682B tablet contains GZR (50 mg), MK-3682 (225 mg), and MK-8408 (30 mg), and is administered as two tablets once daily, for a total daily dose of 100 mg GZR, 450mg MK-3682, and 60mg MK-8408. Non-cirrhotic and cirrhotic, treatment-naïve and pegylated-IFN/RBV (PR) treatment-experienced, GT1-GT6 subjects with or without HIV co-infection have received MK-3682B with or without RBV for 8, 12, or 16 weeks of therapy, depending on the treatment arm.

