5.8 Subject Withdrawal/Discontinuation Criteria

Subjects may withdraw consent at any time for any reason or be dropped from the trial at the discretion of the investigator should any untoward effect occur. In addition, a subject may be withdrawn by the investigator or the Sponsor if enrollment into the trial is inappropriate, the trial plan is violated, or for administrative and/or other safety reasons. Specific details regarding discontinuation or withdrawal procedures; including specific details regarding withdrawal from Future Biomedical Research, are provided in Section 7.1.4 – Other Procedures.

A subject must be discontinued from the trial if:

- The subject or legal representative (such as parent or legal representative) withdraws consent.

A subject must be discontinued from treatment but continue to be monitored in the trial for any of the following reasons:

[Table 10](#) provides reasons why a subject must be discontinued from treatment but should continue to be monitored in the trial, as well as reasons why a subject must be discontinued from treatment and the trial.

Table 10 Discontinuation Scenarios

Reason for Discontinuation Scenario	Action
The subject has a medical condition or personal circumstance which, in the opinion of the investigator and/or Sponsor, places the subject at unnecessary risk through continued participation in the trial or does not allow the subject to adhere to the requirements of the protocol.	Discontinue from Treatment and Trial
Subject meets criteria for HCV virologic breakthrough or rebound (see Section 4.2.3.1.1.2)	Discontinue from Treatment (should continue to monitor in the trial)
Subject becomes pregnant during the trial.	Discontinue from Treatment (should continue to monitor in the trial)
A physician investigator feels it is in the best interest of the subject to discontinue.	Discontinue from Treatment (should continue to monitor in the trial)
The subject's ALT or AST increases to >500 IU/L and is confirmed with repeat test within one week.	Discontinue from Treatment (should continue to monitor in the trial)
The subject's ALT or AST increases to >3x the nadir value, is >3x ULN (confirmed with repeat test within one week), and there is a simultaneous increase in total bilirubin > 2x ULN and/or INR is increased from the baseline value and is >1.5 (unless the subject is on anticoagulation).	Discontinue from Treatment (should continue to monitor in the trial)

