The subject's ALT or AST increases to >3x nadir, is >3x ULN (confirmed with repeat test within one week), and is temporally associated with signs or symptoms of liver inflammation that are of moderate or severe intensity and deemed by the investigator to be at least possibly related to study therapy.	Discontinue from Treatment (should continue to monitor in the trial)
The subject's serum creatinine increases to Grade 3 or higher (>1.8x upper limit of normal), confirmed with repeat test within one week.	Discontinue from Treatment (should continue to monitor in the trial)
The subject's creatinine clearance (eGFR) decreases to <30 mL/min/1.73 m ² , confirmed with repeat test within 1 week. Creatinine clearance will be evaluated as an estimated GFR (eGFR), based on the modification of diet in renal disease (MDRD) equation: $eGFR \text{ (mL/min/1.73 m}^2\text{)} = 175 \times (\text{Scr, std})^{-1.154} \times (\text{Age})^{-0.203} \times (0.742 \text{ if female}) \times (1.212 \text{ if black})$ Scr, std: serum creatinine measured with a standardized assay	Discontinue from Treatment (should continue to monitor in the trial)
The subject has a Grade 4 laboratory AE, or a life-threatening clinical AE, or an AE that results in or prolongs an existing in-subject hospitalization, that is assessed to be a study drug-related laboratory or clinical AE.	Discontinue from Treatment (should continue to monitor in the trial)
SAE assessed by the physician investigator as possibly or probably related to study medication. Investigator may continue the subject in the trial, if it is deemed to be in the best interest of the subject to stay on the study treatment after consultation with Sponsor.	May Discontinue from Treatment (should continue to monitor in the trial)
Failure to comply with the dosing, evaluations, or other requirements of the trial.	May Discontinue from Treatment (should continue to monitor in the trial)

NOTE: Clinical management of HIV-1 virologic failure will be handled by site investigators according to current HIV treatment guidelines and local standard of care. Subjects with HIV virologic failure may continue in the study unless there is a requirement for prohibited concomitant medications (see Section 5.5) to construct a new HIV treatment regimen.

Discontinuation from treatment is “permanent.” Once a subject is discontinued, he/she shall not be allowed to restart treatment.

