7.2.3.2 Events of Clinical Interest

Selected non-serious and serious adverse events are also known as Events of Clinical Interest (ECI) and must be reported to the Sponsor.

For the time period beginning when the consent form is signed until treatment allocation/randomization, any ECI, or follow up to an ECI, that occurs to any subject must be reported within 24 hours to the Sponsor if it causes the subject to be excluded from the trial, or is the result of a protocol-specified intervention, including but not limited to washout or discontinuation of usual therapy, diet, placebo treatment or a procedure.

For the time period beginning at treatment allocation/randomization through 14 days following cessation of treatment, any ECI, or follow up to an ECI, whether or not related to the Sponsor's product, must be reported within 24 hours to the Sponsor, either by electronic media or paper. Electronic reporting procedures can be found in the EDC data entry guidelines. Paper reporting procedures can be found in the Investigator Trial File Binder (or equivalent).

Events of clinical interest for this trial include:

1. an overdose of Sponsor's product, as defined in Section 7.2.1 - Definition of an Overdose for This Protocol and Reporting of Overdose to the Sponsor, that is not associated with clinical symptoms or abnormal laboratory results.
2. first instance of ALT or AST >500 IU/L from the initiation of study therapy through 14 days following treatment.*
3. first instance of ALT or AST >3x nadir AND >3x Upper Limit of Normal (ULN) from the initiation of study therapy through 14 days following treatment.*

*Note: The purpose of the criteria is to specify a threshold of abnormal hepatic tests that may require an additional evaluation for an underlying etiology. The trial site guidance for assessment and follow up of these criteria can be found in the Investigator Trial File Binder (or equivalent).

Additional events of clinical interest for this trial include:

1. first instance of eGFR < 30 mL/min/1.73 m² from the initiation of study therapy through 14 days following treatment. Creatinine clearance will be evaluated as an estimated GFR (eGFR), based on the MDRD equation:

$$\text{eGFR (mL/min/1.73 m}^2\text{)} = 175 \times (\text{Scr, std})^{-1.154} \times (\text{Age})^{-0.203} \times (0.742 \text{ if female}) \times (1.212 \text{ if black})$$

Scr, std: serum creatinine measured with a standardized assay

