8.2 Responsibility for Analyses/In-House Blinding

The statistical analysis of the data obtained from this study will be the responsibility of the Clinical Biostatistics department of the Sponsor.

This trial is being conducted as an open-label study, i.e., subjects, investigators, and Sponsor personnel will be aware of subject treatment assignments after each subject is enrolled and treatment is assigned. Through the course of this open-label study, efficacy and safety analyses may be performed by the Sponsor to monitor trends and facilitate programmatic decisions. In particular, when at least half of the subjects have reached FW4 and/or FW8, initial assessment of SVR₄ and/or SVR₈ may be performed.

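### Neither trial-level safety rule names Table 10's two combined hepatic stop criteria, so such cases at or below 500 IU/L force no pause or termination unless they also meet a general severity item

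*Combined protocol and SAP*

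**What the plan says.** Table 10 in section 5.8 has three hepatic rows, each requiring discontinuation of treatment with continued monitoring in the trial:

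1. ALT or AST above 500 IU/L, confirmed within a week.
2. ALT or AST above 3x nadir and above 3x ULN, confirmed, "and there is a simultaneous increase in total bilirubin > 2x ULN and/or INR is increased from the baseline value" and is above 1.5 (INR part not applied to subjects on anticoagulation).
3. The same confirmed rise with signs or symptoms of liver inflammation "of moderate or severe intensity and deemed by the investigator to be at least possibly related to study therapy".

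Section 5.11.2 terminates the trial when at least 12 subjects (about 5%) in the 12-week arms have any listed event. Its only named hepatic event is "ALT or AST increases to >500 IU/L and is assessed to be study drug related". It also lists both renal rows of Table 10 and a general item: a drug-related Grade 4 laboratory AE, life-threatening AE, hospitalisation or death.

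Section 5.11.1 says that if at least 3 "subjects receiving MK-3682 and MK-8408 experience any of the following, assignment of new subjects into that arm will be paused" until the Sponsor has reviewed the safety data. Its list has drug-related life-threatening events, hospitalisations and deaths, and "Grade 4 laboratory AEs that are assessed to be study drug-related laboratory AEs". It names no organ-specific event, hepatic or renal.

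Section 7.2.3.2 makes the "first instance of ALT or AST >3x nadir AND >3x Upper Limit of Normal (ULN) from the initiation of study therapy" an event of clinical interest (ECI), reportable within 24 hours whether or not related. Section 8.6.2 estimates laboratory ECIs with 95% confidence intervals, by arm and combined. Section 8.2 adds that "efficacy and safety analyses may be performed by the Sponsor to monitor trends and facilitate programmatic decisions".

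**The concern.** The two omitted rows pair a transaminase rise with impaired liver function or with symptoms. The protocol treats them as serious enough to end a subject's treatment permanently. Yet followed as written, any number of drug-related cases of this kind can accrue without forcing a review, provided that each stays at or below 500 IU/L and outside the general severity items. An isolated drug-related ALT above 500 IU/L, by contrast, counts toward termination. No reason is given for carrying over one hepatic row and both renal rows but not the other two hepatic rows.

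The gap matters somewhat more here because Table 1 targets about 60 subjects with compensated cirrhosis (10 + 5 + 15 + 15 + 15), and section 4.1.2.1 names the liver as a potential target organ of MK-3682 in the toxicity studies. The pause rule also leaves its counting unit implicit: the consequence is stated for an arm, but the count of three is not.

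**Working it through.** **Step 1. Side-by-side reading.**

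| Table 10 row | Named in 5.11.1 (pause, at least 3) | Named in 5.11.2 (terminate, at least 12) |
|---|---|---|
| ALT/AST >500 IU/L | No | Yes, if drug-related |
| ALT/AST rise with bilirubin and/or INR | No | No |
| ALT/AST rise with liver symptoms | No | No |
| Creatinine Grade 3 or higher | No | Yes |
| eGFR <30 mL/min/1.73 m² | No | Yes |
| Drug-related Grade 4 laboratory AE, life-threatening AE or hospitalisation | Yes, death added | Yes, death added |

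The combined hepatic rows are named in 0 of 2 instances in each rule. They enter either count only through the last line.

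**Step 2. The plan's own figure.** 12/250 = 4.8%, which agrees with the stated ~5%. No stated number is wrong.

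**Step 3. What adding the rows to the pause list would cost.** The documents give no rate for the combined events, so 1% and 2% per subject are assumptions. The only clinical ALT rate available is 1/240 (section 4.1.2.2.2). It concerns ALT above 5x ULN on three-drug regimens in non-cirrhotic subjects, so it is a different event in a different population. Full enrolment is assumed: four arms of 50 and two of 25.

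With X ~ Binomial(n, p), P50 = P(X ≥ 3) at n = 50 and P25 = P(X ≥ 3) at n = 25, the chance that at least one arm pauses is 1 − (1 − P50)^4 × (1 − P25)^2.

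| Rate p | P50 | P25 | At least one arm paused | At least 3 of 250 (trial-wide) |
|---|---|---|---|---|
| 1/240 | 0.12% | 0.02% | 0.5% | 8.8% |
| 1% (assumed) | 1.38% | 0.20% | 5.8% | 45.7% |
| 2% (assumed) | 7.84% | 1.32% | 29.8% | 87.8% |

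At 1%: 1 − (0.9862)^4 × (0.9980)^2 = 5.8%. These figures cover the two combined rows alone; events above 500 IU/L would add to them.

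**Step 4. What adding the rows to the termination list would do.** Section 5.11.2 is one pooled count, so the effect depends on the rate already counted. P(X ≥ 12) at n = 250 is 0.5% at 2%, 7.6% at 3% and 30.1% at 4%. Adding 1% of subjects to an assumed 2% already counted therefore moves the chance of termination from 0.5% to 7.6%. Adding 1% to an assumed 3% moves it from 7.6% to 30.1%. The combined rows alone give 0.001% at 1% and 0.5% at 2%, but that ignores every other listed event.

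**The case against.** Individual stopping criteria need not all become trial-level criteria, and 5.11.1 consistently uses general severity triggers. The most severe drug-related hepatic cases are already caught by the Grade 4, life-threatening, hospitalisation and death items. Every qualifying rise reaches the Sponsor within 24 hours in an open-label trial. Sections 2.1 and 4.3 commit the Sponsor to careful safety monitoring, and section 7.1.5.7 requires weekly visits until normalisation when a laboratory ECI is present at the last dosing visit. The evidence on risk is reassuring. The toxicity findings were minimal and not considered adverse. The single ALT rise among 240 Part A subjects came "with a pattern consistent with the late ALT increases observed in the Phase 2 and 3 GZR studies", and grazoprevir is not in this regimen. Section 4.3 reports no consistent treatment-related laboratory changes for MK-8408.

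Most of this stands, and it limits the weight of the point. It does not close the gap, because none of these provisions attaches a number of combined hepatic cases to an action.

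A reader might go further and infer that these cases have no trial-level count at all, or go undetected. The documents do not support that: laboratory ECIs are tabulated by arm and overall, and severe drug-related cases count in both rules. A reader might also infer that the rows must go into 5.11.2 at negligible cost. Step 4 shows otherwise, since termination there is automatic once the pooled count is reached.

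**Conclusion.** The point holds in a limited form. Neither trial-level rule names the two combined hepatic criteria, and a case at or below 500 IU/L counts only when it is also drug-related and Grade 4, life-threatening, hospitalised or fatal. What is absent is an action threshold, not detection or tabulation.

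The size of the gap cannot be fixed. The documents give no event rate and no Grade 4 cut-offs for ALT, AST, bilirubin or INR, so the overlap with the Grade 4 item is unknown. The probabilities above measure how often an amended rule would fire at chosen rates; they do not measure harm under the present rule. The text comparison is firm and the rates are assumptions. All 240 Part A subjects were non-cirrhotic, so 1/240 says little about the cirrhotic subjects here. The point is for the sponsor to consider: an inexpensive safety improvement in the pause rule.

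**What to change.** Add the three hepatic rows of Table 10 to the 5.11.1 list by reference, limited to events assessed as study drug-related. All three are needed; otherwise a rise above 500 IU/L would be left out while smaller combined rises counted. The drug-related condition keeps out unrelated events in subjects with cirrhosis or Gilbert's disease. State in 5.11.1 that the count of three is per arm, which is the natural reading of its consequence.

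The change is amendment wording only, because laboratory values, ECI reports and causality assessments are already collected. The price is more enrolment pauses for Sponsor review, at the per-arm rates in Step 3 plus whatever events above 500 IU/L add; subjects tolerating treatment may continue during a pause. A per-arm count is also weaker than a trial-wide one: two cases in each of six arms, 12 in all, would still trigger no pause.

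Adding the combined rows to 5.11.2 should be left as a trade-off for the sponsor, given Step 4. The documents do not state enrolment status, and the Summary of Changes reports that development of the regimen was discontinued. If enrolment is closed, the change is of use only for similar protocols.

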5.11.3 Efficacy Criteria for Stopping Enrollment

- If a total of ≥ 2 out of the first 10 HIV-infected subjects in the PP population across all arms experience confirmed loss of HIV-1 virologic suppression, then no additional HIV/HCV co-infected subjects will be enrolled. Loss of virologic suppression is defined as HIV-1 RNA ≥ 200 copies/mL, confirmed on 2 consecutive tests at least 2 weeks apart in subjects compliant with their HIV ARV therapies. Remaining co-infected subjects who are already on trial treatment would continue HCV treatment regimen while their HIV regimen is being reassessed.
- If a total of ≥ 3 out of the first 10 subjects in the PP population enrolled in a 12-week dosing duration arm experience virologic non-response, rebound, breakthrough or relapse by FW4, no further subjects will be enrolled in that 12-week treatment arm.

